a) Melanoma, PD-L1 positive

- i) Histologically confirmed, unresectable Stage III or Stage IV melanoma, as specified in the American Joint Committee on Cancer (AJCC) staging system.
- ii) Subjects must be either I-O therapy naïve, or may have received and then had disease progression after 1 prior I-O therapy in the advanced or metastatic setting. For subjects who have received prior immuno-oncology therapy, prior treatment with only 1 agent is permitted; subjects who have received combination I-O therapy are excluded. At least 35 subjects in this cohort will be I-O treatment naïve.
- iii) PD-L1 positive subjects, defined as PD-L1 $\geq 1\%$, are eligible for this cohort. PD-L1 status will be determined using tissue acquired from the mandatory pre-treatment biopsy. Results of previous PD-L1 status testing must be documented if available. (Note: If the PD-L1 status from the pre-treatment biopsy is not available prior to the start of treatment, subjects will be retrospectively assigned to the correct cohort once the result is available.)
- iv) BRAF (V600) mutation status must be known. Both BRAF-mutated and WT subjects are permitted in this cohort

b) Melanoma, PD-L1 negative

- i) Histologically confirmed, unresectable Stage III or Stage IV melanoma, as specified in the American Joint Committee on Cancer (AJCC) staging system.

- ii) Subjects must be either I-O therapy naïve, or may have received and then had disease progression after 1 prior I-O therapy in the advanced or metastatic setting. For subjects who have received prior immuno-oncology therapy, prior treatment with only 1 agent is permitted; subjects who have received combination I-O therapy are excluded. At least 20 subjects in this cohort will be I-O treatment naïve
- iii) PD-L1 negative subjects, defined as PD-L1 <1%, are eligible for this cohort. PD-L1 status will be determined using tissue acquired from the mandatory pre-treatment biopsy. Results of previous PD-L1 status testing must be documented if available. (Note: If the PD-L1 status from the pre-treatment biopsy is not available prior to the start of treatment, subjects will be retrospectively assigned to the correct cohort once the result is available.)
- iv) BRAF (V600) mutation status must be known. Both BRAF-mutated and WT subjects are permitted in this cohort

c) NSCLC PD-L1 positive

- i) Histologically or cytologically confirmed, advanced (ie, unresectable or metastatic) NSCLC of either squamous or non-squamous histology.
- ii) Subjects must be either treatment naïve in the advanced setting or may have received and then had disease progression after at least one line of prior therapy. For subjects who received chemotherapy or a TKI as first line therapy, no subsequent therapy is permitted. For subjects who received PD-(L)1 targeted therapy as first line treatment, this may have been given either as monotherapy or in combination with chemotherapy only; no prior I-O combination therapy is permitted. Subjects who received PD-(L)1 targeting monotherapy as first-line treatment may also have received chemotherapy or TKI therapy after disease progression. At least 25 subjects in this cohort will be treatment naïve in the advanced setting and at least 10 subjects IO-therapy naive.
- iii) EGFR and ALK status must be known. KRAS mutational status should be documented if available.
 - (1) EGFR and ALK may be unknown for subjects with squamous cell histology.
 - (2) Subjects with a sensitizing EGFR mutation or ALK/ROS1 rearrangement must have received appropriate therapy directed at the mutation or rearrangement
- iv) PD-L1 positive subjects, defined as PD-L1 $\geq 1\%$, are eligible for this cohort. PD-L1 status will be determined using tissue acquired from the mandatory pre-treatment biopsy. Results of previous PD-L1 status testing must be documented if available. (Note: If the PD-L1 status from the pre-treatment biopsy is not available prior to the start of treatment, subjects will be retrospectively assigned to the correct cohort once the result is available.)

d) NSCLC PD-L1 negative

- i) Histologically or cytologically confirmed, advanced (ie, unresectable or metastatic) NSCLC of either squamous or non-squamous histology.
- ii) Subjects must be either treatment naïve in the advanced setting or may have received and then had disease progression after at least one line of prior therapy. For subjects who received chemotherapy or a TKI as first line therapy, no subsequent therapy is permitted. For subjects who received PD-(L)1 targeted therapy as first line treatment,

this may have been given either as monotherapy or in combination with chemotherapy only; no prior I-O combination therapy is permitted. Subjects who received PD-(L)1 targeting monotherapy as first-line treatment may also have received chemotherapy or TKI therapy after disease progression. At least 25 subjects in this cohort will be treatment naïve in the advanced setting and at least 10 subjects IO-therapy naive.

- iii) EGFR and ALK status must be known. KRAS mutational status should be documented if available.
 - (1) EGFR and ALK may be unknown for subjects with squamous cell histology.
 - (2) Subjects with a sensitizing EGFR mutation or ALK/ROS1 rearrangement must have received appropriate therapy directed at the mutation or rearrangement.
- iv) PD-L1 negative subjects, defined as PD-L1 < 1%, are eligible for this cohort. PD-L1 status will be determined using tissue acquired from the mandatory pre-treatment biopsy. Results of previous PD-L1 status testing must be documented if available. (Note: If the PD-L1 status from the pre-treatment biopsy is not available prior to the start of treatment, subjects will be retrospectively assigned to the correct cohort once the result is available.)

e) Bladder cancer

- i) Evidence of metastatic or surgically unresectable transitional cell carcinoma of the urothelium involving the bladder, urethra, ureter, or renal pelvis.
- ii) Progression or recurrence after treatment with:
 - At least 1 platinum-containing chemotherapy regimen for metastatic or surgically unresectable locally advanced urothelial cancer OR
 - Within 12 months of peri-operative (neo-adjuvant or adjuvant) treatment with a platinum agent in the setting of cystectomy for localized muscle-invasive urothelial cancer.
- iii) Subjects may have received prior I-O therapies, but at least 30 subjects in this cohort will be I-O therapy naive.

f) Mixed Tumor Type Cohort (Ipi 1Q8)

- i) Subjects must have tumor types included in Part 2 and meet inclusion criteria defined for each tumor type in Part 2
- ii) All subjects must be I-O therapy naive.

3) General Inclusion Criteria:

- a) Eastern Cooperative Oncology Group performance status of ≤ 1
- b) Ability to swallow pills or capsules.
- c) Presence of at least 1 lesion with measurable disease as defined by RECIST v1.1 for solid tumors and IWG for lymphomas for response assessment. Subjects with lesions in a previously irradiated field as the sole site of measurable disease will be permitted to enroll provided the lesion(s) have demonstrated clear progression and can be measured accurately.
- d) Subjects with prior exposure to therapy with any agent specifically targeting checkpoint pathway inhibition (such as anti-PD-[L]1, anti-PDL-2, anti-LAG-3, and anti-CTLA-4 antibodies) are permitted after a washout period of any time greater than 4 weeks from

the last treatment.**Note that certain expansion cohorts do not allow prior treatment with immunotherapy agents, including I-O naïve melanoma and NSCLC. See tumor-specific eligibility criteria above. In addition, the 4-week washout period is not required for the following Part 2 expansion cohorts: Melanoma, prior anti-PD-(L)1 and prior anti-PD-(L)1/anti-CTLA-4 combination and NSCLC, prior anti-PD-(L)1 or for subjects in Part 3 Melanoma and NSCLC cohorts with prior IO-treatment.

Note: (i) Subjects who experienced prior Grade 1 to 2 checkpoint therapy-related immune-mediated AEs must have confirmed recovery from these events at the time of study entry, **other than endocrinopathies treated with supplementation**, as documented by resolution of all related clinical symptoms, abnormal findings on PE, and/or associated laboratory abnormalities. Where applicable, these subjects must also have completed steroid tapers for treatment of these AEs by a minimum of 14 days prior to commencing treatment with study drug.

(ii) Eligibility of subjects with prior \geq Grade 3 checkpoint therapy-related immune AEs, will be considered on a case-by-case basis after discussion with the Medical Monitor (eg, asymptomatic isolated Grade 3 lipase elevations without clinical or radiological features of pancreatitis will be permitted to enroll).

- e) Subjects with prior therapy with any agent specifically targeting T-cell co-stimulation pathways such as anti-glucocorticoid-induced TNFR family related gene antibody, anti-CD137, anti-OX40 antibody are permitted after a washout period of any time greater than 4 weeks from the last treatment.
- f) Prior palliative radiotherapy must have been completed at least 2 weeks prior to first dose of study drug. Subjects with symptomatic tumor lesions at baseline that may require palliative radiotherapy within 4 weeks of first dose of study drug are strongly encouraged to receive palliative radiotherapy prior to enrollment.
- g) All subjects must have archival FFPE tumor tissue available. This must be a block or 20 FFPE unstained slides (fewer slides may be acceptable with the approval of the medical monitor, but generally at least 15 will be required). With Amendment 14, archival tissues from subjects in Parts 1 and 3 may be of any age, while for all other subjects blocks must have been obtained less than 1 year prior to enrollment, and FFPE slides must have been cut less than 4 months prior to enrollment; if archival tissue meeting these age requirements is not available, subjects must undergo fresh biopsies as detailed below. Tumor samples for archival tissue obtained by fine needle aspirate/biopsy or from bone lesion are not acceptable. Subjects must consent to the acquisition of this archival tissue. In limited circumstances, subjects with newly diagnosed, untreated melanoma and NSCLC without archival tissue available may be permitted to enroll after permission is obtained from the Medical Monitor or Study Director, but will be required to undergo fresh biopsy.
- h) All subjects in Parts 1 and 3 (as well as subjects in other parts without archival tissue meeting the requirements above) will be required to undergo mandatory pre-treatment biopsies. All subjects will be required to undergo an on-treatment biopsy, unless considered to pose unacceptable clinical risk, as judged by the investigator and in consultation with the medical monitor/study director.

- i) Pre-treatment tissue must be collected prior to first dose of study drug. Recent fresh samples (frozen and FFPE) obtained prior to start of screening that meet biomarker requirements ([Section 5.7.2](#)) of the study as determined by the Study Director or Medical Monitor may be substituted for fresh biopsies, after permission from the Study Director or Medical Monitor is obtained.
- ii) The tumor tissue specimen must be a core needle, excisional or incisional biopsy. Fine needle biopsies, drainage of pleural effusions with cytospins, or punch biopsies are not considered adequate for biomarker review and randomization. Biopsies of bone lesions that do not have a soft tissue component or decalcified bone tumor samples are also not acceptable.
- iii) Where possible, the biopsied lesion should be distinct from target lesions being evaluated for radiologic response, and the same lesion should be used for both the baseline and on-treatment sampling.
- i) Blood methemoglobin levels within the ULN
- j) Adequate marrow function for subjects with solid tumor histologies as defined by the following:
 - i. White blood cell (WBC) $\geq 2000/\mu\text{L}$ (stable off any growth factor within 4 weeks of first study drug administration)
 - ii. Neutrophils $\geq 1500/\mu\text{L}$ (stable off any growth factor within 4 weeks of first study drug administration)
 - iii. Platelets $\geq 100 \times 10^3/\mu\text{L}$ (transfusion to achieve this level is not permitted within 2 weeks of first study drug administration)
 - iv. Hemoglobin $\geq 8.5 \text{ g/dL}$ (transfusion to achieve this level is not permitted within 2 weeks of first study drug administration)
- k) Adequate marrow function for subjects with B-cell NHL and HL malignancies as defined by the following:
 - i. Absolute neutrophil count $\geq 750/\mu\text{L}$ (no WBC growth factors for prior 14 days)
 - ii. Platelets $\geq 50 \times 10^3/\mu\text{L}$ (no platelet transfusions for prior 14 days)
 - iii. Hemoglobin $> 8.0 \text{ g/dL}$ (no RBC transfusions for prior 7 days)
- l) Adequate other organ functions as defined by the following:
 - i. ALT and AST $\leq 3 \times$ institutional ULN
 - ii. Total bilirubin $\leq 1.5 \times$ institutional ULN (except subjects with Gilbert's Syndrome who must have normal direct bilirubin)
 - iii. [This criterion is no longer applicable]
 - iv. Normal thyroid function, subclinical hypothyroidism (thyroid-stimulating hormone [TSH] $< 10 \text{ mIU/mL}$), or have controlled hypothyroidism on appropriate thyroid supplementation
 - v. Serum creatinine $\leq 1.5 \times$ ULN or creatinine clearance (CrCl) $\geq 40 \text{ mL/min}$ (measured using the Cockcroft-Gault formula below):

$$\text{Female CrCl} = \frac{(140 - \text{age in years}) \times \text{weight in kg} \times 0.85}{72 \times \text{serum creatinine in mg/dL}}$$

$$\text{Male CrCl} = \frac{(140 - \text{age in years}) \times \text{weight in kg} \times 1.00}{72 \times \text{serum creatinine in mg/dL}}$$

vi. Ability to comply with treatment, PK, and pharmacodynamic sample collection, and required study follow-up.

Subject Re-enrollment: This study permits the re-enrollment of a subject who has discontinued the study as a pre-treatment failure (eg, subject has not been treated). If re-enrolled, the subject must be re-consented.

4) Age and Reproductive Status

- a) Men and women, ages \geq 18 years at the time of informed consent
- b) Women of childbearing potential (WOCBP) must have a negative serum or urine pregnancy test (urine pregnancy test: minimum sensitivity 25 IU/L or equivalent units of human chorionic gonadotropin) within 24 hours prior to the start of study drug.
- c) Women must not be breastfeeding
- d) WOCBP must agree to follow instructions for method(s) of contraception for the duration of treatment with study drug(s) plus an additional 5 months (approximately 23 weeks) post-treatment completion.
- e) Males who are sexually active with WOCBP must agree to use a synthetic or latex condom during sexual activity for the duration of treatment with study treatment plus an additional 7 months after the last dose of the study treatment (ie, 90 days [the duration of sperm turnover] plus the time required for nivolumab to undergo approximately 5 half-lives). This criterion applies to azoospermic males as well. In addition, male subjects must be willing to refrain from sperm donation during this time.
- f) WOCBP who are continuously not heterosexually active are exempt from contraceptive requirements. However, WOCBP must still undergo pregnancy testing as described in this section.

Investigators shall counsel WOCBP and male subjects who are sexually active with WOCBP on the importance of pregnancy prevention and the implications of an unexpected pregnancy. Investigators shall advise WOCBP and male subjects who are sexually active with WOCBP on the use of highly effective methods of contraception ([Appendix 11](#)). Highly effective methods of contraception have a failure rate of $< 1\%$ when used consistently and correctly. **Hormonal contraceptives are not highly effective methods of contraception for subjects receiving BMS-986205 in this study who are WOCBP.**

3.3.2 *Exclusion Criteria*

1) Target Disease Exceptions

- a) Subjects with known or suspected CNS metastases, untreated CNS metastases, or with the CNS as the only site of disease are excluded. However, subjects with controlled brain metastases will be allowed to enroll. Controlled brain metastases are defined as no radiographic progression for at least 4 weeks following radiation and/or surgical treatment (or 4 weeks of observation if no intervention is clinically indicated), off of steroids for at least 2 weeks, and no new or progressive neurological signs and symptoms. Please note: SCCHN subjects with direct extension of tumor through the base of skull will not be excluded, as they are considered distinct from hematogenously spread parenchymal brain metastasis.
- b) Ocular melanoma
- c) [This criterion is no longer applicable]

2) Medical History and Concurrent Diseases

- a) Subjects with a history or presence of G6PD deficiency, cytochrome b5 reductase deficiency, or other diseases that put them at risk of methemoglobinemia.
- b) History of congenital or autoimmune hemolytic disorders.

If subject has history of transient acquired hemolytic anemia, discuss with Medical Monitor for study eligibility.

- c) History or presence of hypersensitivity or idiosyncratic reaction to methylene blue.
- d) Subjects with a prior malignancy are excluded (except non-melanoma skin cancers and in situ cancers such as the following: bladder, colorectal, cervical/dysplasia, melanoma, or breast). Subjects with other second malignancies diagnosed more than 2 years ago who have received therapy with curative intent with no evidence of disease during the interval who are considered by the investigator to present a low risk for recurrence will be eligible.
- e) Other active malignancy requiring concurrent intervention.
- f) Prior organ allograft or allogeneic bone marrow transplantation.
- g) Any anti-cancer therapy (eg, chemotherapy, biologics, vaccines, or hormonal treatment) including investigational drugs within 4 weeks prior to the first dose of study drug administration, except for non-cytotoxic therapies, for which at least 4 weeks or 5 half-lives (whichever is shorter) must have elapsed between last dose and first treatment with any study drugs; if 5 half-lives is shorter than 4 weeks, agreement with the Medical Monitor must be obtained. ****Note that this criterion does not apply for anti-PD-(L)1 therapy in the following Part 2 expansion cohorts: Melanoma, prior anti-PD-(L)1 and anti-PD-(L)1/anti-CTLA-4 combination and NSCLC, prior anti-PD-(L)1.**
- h) Prior therapy with an IDO inhibitor.
- i) Subjects with active, known or suspected autoimmune disease. Subjects with vitiligo, type I diabetes mellitus, residual hypothyroidism due to autoimmune condition only requiring hormone replacement, euthyroid subjects with a history of Grave's disease

(subjects with suspected autoimmune thyroid disorders must be negative for thyroglobulin and thyroid peroxidase antibodies and thyroid stimulating immunoglobulin prior to first dose of study drug), psoriasis not requiring systemic treatment, or conditions not expected to recur in the absence of an external trigger are permitted to enroll.

j) Subjects with a condition requiring systemic treatment with either corticosteroids (> 10 mg daily prednisone equivalents) or other immunosuppressive medications within 14 days of study drug administration except for adrenal replacement steroid doses > 10 mg daily prednisone equivalent in the absence of active autoimmune disease.

Note: Treatment with a short course of steroids (< 5 days) up to 7 days prior to initiating study drug is permitted.

k) Requirement for daily supplemental oxygen.

l) Uncontrolled or significant cardiovascular disease including, but not limited to, any of the following:

- i) Myocardial infarction or stroke/transient ischemic attack within the past 6 months
- ii) Uncontrolled angina within the past 3 months
- iii) Any history of clinically significant arrhythmias (such as ventricular tachycardia, ventricular fibrillation, or torsades de pointes)
- iv) QT interval corrected for heart rate using Fridericia's formula (QTcF) prolongation > 480 msec
- v) History of other clinically significant heart disease (eg, cardiomyopathy, congestive heart failure with New York Heart Association functional classification III-IV, pericarditis, significant pericardial effusion, or myocarditis)
- vi) Cardiovascular disease-related requirement for daily supplemental oxygen therapy

m) History of any chronic hepatitis as evidenced by the following:

- i) Positive test for hepatitis B surface antigen
- ii) Positive test for qualitative hepatitis C viral load (by polymerase chain reaction [PCR])

Note: *Subjects with positive hepatitis C antibody and negative quantitative hepatitis C by PCR are eligible. History of resolved hepatitis A virus infection is not an exclusion criterion*

n) History of other preexisting liver disease (eg, NAFLD).

o) Evidence of active infection ≤ 7 days prior to initiation of study drug therapy (does not apply to viral infections that are presumed to be associated with the underlying tumor type required for study entry).

p) Known history of testing positive for human immunodeficiency virus (HIV) or known acquired immunodeficiency syndrome (AIDS). Note: Testing for HIV must be performed at sites where mandated by local requirements.

- q) Evidence or history of active or latent tuberculosis infection including PPD recently converted to positive; chest x-ray with evidence of infectious infiltrate; and recent unexplained changes in fever/chill patterns.
- r) Any major surgery within 4 weeks of study drug administration. Subjects must have recovered from the effects of major surgery or significant traumatic injury at least 14 days before the first dose of study drug.
- s) All toxicities attributed to prior anti-cancer therapy other than alopecia and fatigue must have resolved to Grade 1 (National Cancer Institute Common Terminology Criteria for Adverse Events [NCI CTCAE] v4.03) or baseline before administration of study drug. Subjects with toxicities attributed to prior anti-cancer therapy that are not expected to resolve and result in long lasting sequelae, such as neuropathy after platinum-based therapy, are permitted to enroll.
- t) Subjects with history of life-threatening toxicity related to prior immune therapy (eg. anti-CTLA-4 or anti-PD-1/PD-L1 treatment or any other antibody or drug specifically targeting T-cell co-stimulation or immune checkpoint pathways) except those that are unlikely to re-occur with standard countermeasures (eg, hormone replacement after adrenal crisis)
- u) Concomitant use of strong inhibitors of CYP3A4 or strong inducers of CYP3A4 (see [Appendix 7](#)).
 - i) Per Amendment 14, also includes strong inhibitors/inducers of CYP1A2
- v) Use of nononcology vaccines containing live virus for prevention of infectious diseases within 12 weeks prior to study drug. The use of inactivated seasonal influenza vaccines (eg, Fluzone[®]) will be permitted on study without restriction.
- w) Use of packed red blood cells or platelet transfusion within 2 weeks prior to the first dose of study drug as specified in [Section 3.3.1](#), j and k.
- x) A known or underlying medical condition that, in the opinion of the investigator or Sponsor, could make the administration of study drug hazardous to the subjects or could adversely affect the ability of the subject to comply with or tolerate the study.
- y) Subjects with confirmed or suspected serotonin syndrome
- z) Subjects with active ILD/pneumonitis or with recent history of ILD/ pneumonitis requiring steroids (excluding radiation pneumonitis)
- aa) Subjects with impairment of gastrointestinal function or gastrointestinal disease, or other conditions known to interfere significantly with the absorption of oral medication, per investigator judgement

3) Physical and Laboratory Test Findings

- a) Positive test for hepatitis B virus surface antigen or hepatitis C ribonucleic acid (RNA). (Subjects with positive hepatitis C antibody and negative quantitative hepatitis C by PCR are eligible.) Additional testing or substitute testing per institutional guidelines to rule out infection is permitted.
 - i) [This criterion is no longer applicable]

- ii) [This criterion is no longer applicable]
- b) Any of the following on 12-lead ECG prior to study drug administration, confirmed by repeat:
 - i) $QRS \geq 120$ msec, except right bundle branch block
 - ii) $QTcF \geq 480$ msec, except right bundle branch block
- c) Second or third degree heart block at Screening (QTc substudy only)

4) Allergies and Adverse Drug Reaction

- a) History of allergy to nivolumab (all study parts) or ipilimumab (Part 3 only).
- b) History of any significant drug allergy (such as anaphylaxis or hepatotoxicity) to prior anti-cancer immune-modulating therapies (eg, checkpoint inhibitors and T-cell co-stimulatory antibodies).

5) Other Exclusion Criteria

- a) Prisoners or subjects who are involuntarily incarcerated.
- b) Subjects who are compulsorily detained for treatment of either a psychiatric or physical (eg, infectious disease) illness.
- c) Inability to comply with restrictions and prohibited activities/treatments as listed in [Section 3.4](#).

Eligibility criteria for this study have been carefully considered to ensure the safety of the study subjects and that the results of the study can be used. It is imperative that subjects fully meet all eligibility criteria.

3.3.3 *Women of Childbearing Potential*

WOCBP is defined as any female who has experienced menarche, who has not undergone surgical sterilization (hysterectomy or bilateral oophorectomy), and who is not postmenopausal. Menopause is defined as 12 months of amenorrhea in a woman over age 45 in the absence of other biological or physiological causes. In addition, females under the age of 55 years must have a documented serum follicle stimulating hormone (FSH) level > 40 mIU/mL to confirm menopause.

Females treated with hormone replacement therapy (HRT) are likely to have artificially suppressed FSH levels and may require a washout period in order to obtain a physiologic FSH level. The duration of the washout period is a function of the type of HRT used. The durations of the washout periods below are suggested guidelines, and the investigators should use their judgment in checking serum FSH levels.

- 1 week minimum for vaginal hormonal products (eg, rings, creams, gels)
- 4 weeks minimum for transdermal products
- 8 week minimum for oral products

Other parenteral products may require washout periods as long as 6 months. If the serum FSH level is > 40 mIU/mL at any time during the washout period, the woman can be considered postmenopausal.

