Once the initial safety and tolerability have been established independently for each regimen based on the safety cohorts, enrollment will then begin in expansion cohorts for further evaluation of safety and tolerability, as well as preliminary evaluation of anti-tumor efficacy. In the expansion cohorts, BMS-986205 will be administered at a dose determined to be tolerable in combination with each nivolumab and ipilimumab regimen. Each BMS-986205 and nivolumab/ipilimumab combination regimen will be evaluated in tumor-specific cohorts based on the tumor type evaluated in the safety cohorts. The Ipi 1Q8 regimen will also be evaluated in a mixed tumor-type cohorts which may incorporate tumor types evaluated in Part 2.

The 3 tumor types for tumor-restricted cohorts will be melanoma, NSCLC, and bladder. As all subjects in these disease-specific cohorts will be receiving agents (nivolumab and ipilimumab) with known anti-tumor activity in those tumor types, a single-stage design will be utilized for each of these tumor types. Approximately 40 subjects will be treated in each of the following expansion cohorts: melanoma PD-L1 positive, melanoma PD-L1 negative, NSCLC PD-L1 positive, NSCLC PD-L1 negative, and bladder; this is to allow for the exploration of early efficacy signals of BMS-986205 in combination with both nivolumab and ipilimumab in relevant subpopulations. In each NSCLC expansion cohort, approximately 10 subjects will be IO-treatment naive, 25 will be treatment-naive, and 5 IO-therapy experienced. In the melanoma cohorts, approximately 35 will be treatment naïve in the advanced setting and 5 will be IO-therapy experienced in each cohort. In the bladder expansion cohort in Part 3, at least 30 subjects will be I-O therapy naive.

A mixed tumor type expansion cohort will also be evaluated, using the same regimen as in the melanoma safety cohort, Ipi 1Q8W. The purpose of this cohort is to obtain preliminary safety,

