8.3 Endpoints

8.3.1 Primary Endpoint(s)

- The primary objective of this study is to establish safety, tolerability, and the MTD/MAD/alternate dose. The assessment of safety will be based on the incidence of AEs, SAEs, AEs leading to discontinuation, and deaths. In addition, clinical laboratory test abnormalities will be examined. AEs and laboratory values will be graded according to the NCI CTCAE v4.03.
- The co-primary objective, anti-tumor activity of BMS-986205 in combination with nivolumab in Part 2 (dose expansion) and BMS-986205 in combination with both nivolumab and ipilimumab in Part 3, will be measured by ORR, DoR, and PFSR based on RECIST v1.1 for solid tumors or IWG for blood tumor. For Parts 1 and 2, disease assessment with CT and/or MRI as appropriate will be performed at baseline, end of Cycle 2, and every 8 weeks. For Part 3, in the melanoma cohorts, the first tumor assessment will occur at Week 12 (\pm 1 week); subsequent imaging will be every 8 weeks thereafter during the treatment period; for NSCLC, imaging assessments will occur every 6 weeks during the treatment period; for bladder, imaging assessments will occur every 6 weeks during the treatment period up to 24 weeks, and then occur every 12 weeks thereafter during the treatment period. For all study parts, assessments continue every 12 weeks for the first year after the EOT visit, and then every 6 months thereafter, up to 2 years following the EOT visit until disease progression per RECIST v1.1 or IWG, or until confirmed disease progression for subjects treated beyond progression (defined as an additional 10% or greater increase in tumor burden volume from time of initial progression including all target lesions and new measurable lesions), at the completion of follow-up, or until subjects withdraw from the study.
- Best overall response (BOR) is defined as the best response designation over the study as a whole, recorded between the dates of first dose until the last tumor assessment prior to subsequent therapy. CR or PR determinations included in the BOR assessment must be confirmed by a second scan performed no less than 4 weeks after the criteria for response are first met. For those subjects who have surgical resection, only presurgical tumor assessments will be considered in the determination of BOR.
- ORR is defined as the proportion of all treated subjects whose BOR is either a CR or PR.

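### Part 3 PD-L1-negative melanoma: the eligibility floor of 20 I-O-naive subjects does not match the planned 35 treatment-naive, and the permitted mix could lower the all-treated ORR by about 9 to 20 points

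*Combined protocol and SAP*

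**What the plan says.** **Design text.** Section 3.1.7 gives the cohort size: "Approximately 40 subjects will be treated in each of the following expansion cohorts", with PD-L1-positive and PD-L1-negative melanoma listed separately. On make-up it says "In the melanoma cohorts, approximately 35 will be treatment" naive in the advanced setting, "and 5 will be IO-therapy experienced in each cohort". The synopsis and Section 8.1.3 repeat this. Section 8.1.3 then sets the melanoma benchmark on 35 treatment-naive subjects: 22 responses of 35, against a historical 58.0%.

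**Eligibility text.** Section 3.3.1 gives a separate quota for each Part 3 cohort:

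- PD-L1-positive melanoma: "At least 35 subjects in this cohort will be I-O treatment" naive.
- PD-L1-negative melanoma: "At least 20 subjects in this cohort will be I-O treatment" naive.
- NSCLC, either PD-L1 group: at least 25 treatment-naive "in the advanced setting and at least 10 subjects IO-therapy naive". Sections 3.1.7 and 8.1.3 plan 25 treatment-naive, 10 I-O-naive and 5 I-O-experienced.
- Bladder: "at least 30 subjects in this cohort will be I-O therapy naive", the same number as the design.

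**Analysis text.** In Section 8.3.1, "ORR is defined as the proportion of all treated subjects whose BOR is either a CR or PR". Section 8.4.2 reports ORR by treatment, dose level and tumor type; prior I-O status is not named. Section 8.4.1 lists demographic and body-size variables, not prior therapy.

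**The concern.** For PD-L1-negative melanoma the two parts of the protocol cannot both describe the intended cohort. Section 3.3 presents the eligibility criteria as mandatory and without exceptions, so a cohort with 20 I-O-experienced subjects breaks no entry rule, although the design foresees 5. No reason is given for treating the two PD-L1 cohorts differently.

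The populations counted also differ. The design and the benchmark count subjects untreated in the advanced setting; the eligibility quotas count subjects without prior I-O therapy. A subject previously given BRAF- or MEK-targeted therapy or chemotherapy can be I-O-naive without being treatment-naive. The Part 2 I-O-naive melanoma cohorts (6a and 6b) bar prior systemic therapy in the unresectable or metastatic setting; the Part 3 melanoma criteria contain no such bar.

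Anti-tumor activity is part of the Part 3 primary objective. If the mix drifts, the all-treated ORR drifts with it, and the planned tabulations would not show why.

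**Working it through.** **1. The plan's own figure.** Section 8.1.3 says that 22 of 35 gives an 80% Clopper-Pearson interval wholly above 58.0%. The lower limit is the 10% quantile of Beta(x, n − x + 1). For 22/35 the interval is 50.6% to 73.9%, so the statement does not reproduce. The smallest count that clears 58% is 25/35 (lower limit 59.4%). That error needs its own correction; here 25/35 serves as the reference. The other two Part 3 benchmarks do reproduce: 16/25 has lower limit 49.2% (above 45.3%) and 16/30 has 40.2% (above 38.5%).

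**2. Inputs for the mix.**

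- Planned mix 35/5 of 40 (3.1.7, 8.1.3); mix permitted at the floor 20/20 of 40 (3.3.1).
- ORR in naive subjects: 58% (8.1.3), or 54.8% for PD-L1-negative tumors on nivolumab plus ipilimumab (1.1.5.2).
- ORR in I-O-experienced subjects: **an assumption**, because no triplet rate is given. The values tried are 10% and 30% (historic and target rates after anti-PD-(L)1, Table 8.1.2-1), 5% and 20% (the same after anti-PD-(L)1 and anti-CTLA-4), and 32% (nivolumab arm of the trial against chemotherapy in 1.1.5.2, whose title in the reference list names progression after anti-CTLA-4). The 5% and 20% rates are sensitivity values only, since prior I-O combination therapy is excluded from Part 3 melanoma.

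**3. Formula.** All-treated ORR = (n_naive × p_naive + n_exp × p_exp) / 40. The fall from 35/5 to 20/20 is (15/40) × (p_naive − p_exp) = 0.375 × (p_naive − p_exp).

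At 58% and 10%: (35 × 58 + 5 × 10)/40 = 52.0%; (20 × 58 + 20 × 10)/40 = 34.0%; fall 18.0 points.
At 54.8% and 10%: 49.2% and 32.4%; fall 16.8 points.

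| ORR assumed in experienced | Fall, naive 58% | Fall, naive 54.8% |
|---|---|---|
| 5% | 19.88 | 18.68 |
| 10% | 18.00 | 16.80 |
| 20% | 14.25 | 13.05 |
| 30% | 10.50 | 9.30 |
| 32% | 9.75 | 8.55 |

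The range is about 9 to 20 points, with no change in drug effect.

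**4. Benchmark denominator.** With 20 naive subjects the smallest count whose 80% lower limit exceeds 58% is 15/20 (75%; lower limit 58.5%), against 25/35 (71%). The floor counts I-O-naive subjects, so the number of treatment-naive subjects could be below 20.

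**5. NSCLC.** A subject untreated in the advanced setting will ordinarily also be I-O-naive, so 25 such subjects meet both floors. That leaves 40 − 25 = 15 places open to I-O-experienced subjects, against 5 planned. I attach no ORR shift: the ten displaced subjects would be previously treated but I-O-naive, and the plan states no triplet response rate for them.

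**The case against.** The strongest reply is that a floor of 20 is compatible with a plan of about 35: it permits drift and does not require it, and the planned 5 experienced subjects per cohort are stated several times elsewhere. The cohorts are descriptive, single-arm and without formal hypotheses. For NSCLC, 25 + 10 + 5 = 40 in Section 3.1.7 makes the intended exclusive groups clear. All of this stands and limits the severity. It does not remove the conflict, because the mandatory criteria contain a number that the design does not.

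Four stronger readings are tempting but not supported:

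- *That the shift is 18 points.* This needs the 10% rate, which is a Part 2 figure for nivolumab with BMS-986205 after recent progression on anti-PD-(L)1. Part 3 admits progression after any one I-O agent and adds ipilimumab. The 58% is not specific to PD-L1-negative tumors.
- *That Part 3 quotas fail in general.* The bladder floor equals the design, the PD-L1-positive melanoma floor matches in number, and the mixed cohort is I-O-naive throughout.
- *That the melanoma benchmark would be diluted, or a PD-L1 comparison biased.* The benchmark is confined to treatment-naive subjects, so only its denominator is at risk. Section 8.4.2 specifies no comparison between PD-L1 cohorts; a misleading contrast could arise only from informal reading.
- *That IVRS would enforce the wrong quota, or could enforce a corrected one.* Section 4.4 describes subject numbering and treatment-group assignment, not quotas. Section 3.3.1 also lets PD-L1 status be assigned after treatment starts.

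**Conclusion.** The inconsistency is real and confined mainly to one cohort. For PD-L1-negative melanoma, Section 3.3.1 requires 20 I-O-naive subjects where the synopsis and Sections 3.1.7 and 8.1.3 plan about 35 treatment-naive. If enrolment ran to the floor, the all-treated ORR would be about 9 to 20 points below that of the planned mix. This rests on assumed rates of 5% to 32% in I-O-experienced subjects and 54.8% or 58% in naive subjects, with no difference in drug effect. The treatment-naive benchmark keeps its meaning but could lose 15 or more of its 35 subjects. The mismatch of terms also touches the PD-L1-positive cohort, and the overlapping NSCLC floors are a secondary wording fault. The point should be fixed, but it affects interpretation rather than error rates and does not undermine the design.

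**What to change.** - Reconcile the PD-L1-negative melanoma floor in Section 3.3.1 with the synopsis and Sections 3.1.7 and 8.1.3. Either align it to about 35 or, if 20 was intended, restate the planned make-up and the benchmark denominator and give the reason. The documents do not show which number was meant.
- Use one term, treatment-naive in the advanced setting, for both melanoma quotas and the benchmark.
- Word the NSCLC groups as mutually exclusive in Section 3.3.1 and in Sections 3.1.7 and 8.1.3: treatment-naive, previously treated but I-O-naive, and I-O-experienced.
- Add prior I-O status to the Part 3 ORR reporting in Section 8.4.2.

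The cost is wording and one extra tabulation; total sample size is unchanged. A higher floor may slow accrual of treatment-naive PD-L1-negative melanoma. Because PD-L1 assignment can be retrospective, the quotas must be monitored during enrolment and cannot be fully enforced at entry.
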